The primary objective of Part 2 is to assess the long-term safety and tolerability of ZX008 in children and adults with LGS with regard to AEs, laboratory parameters, physical examination, neurological examination, vital signs, ECG, ECHO, body weight, and BMI.

The number and percentage of subjects who experience treatment emergent AEs will be displayed by body system and preferred term using MedDRA. Summaries in terms of severity and relationship to study drug will also be provided. SAEs will be summarized separately in a similar manner. Laboratory tests, vital signs, physical examinations, neurological examinations, ECG, ECHO, cognition and body weight will be summarized using appropriate methods.

Effectiveness will be assessed by the change from baseline (prior to randomization into Part 1) in DSF. The DSF per 28 days will be calculated as the number of seizures that result in drops divided by the number of days in the period and multiplied by 28. The change in DSF during the first 12 months of

ZX008 (Fenfluramine Hydrochloride)

ZX008-1601 Clinical Study PA 4.0 (Japan) 25 July 2022

Part 2 OLE Treatment Period will be calculated as the difference between DSF during the OLE and the baseline DSF measured prior to randomization in Part 1. Both the mean and median percent change in DCF will be presented and the statistical significance of the percent change will be assessed using a Wilcoxon signed-rank test. Other secondary assessments will be compared to baseline from prior to Part 1, or by visit throughout Part 1 and the first 12 months of Part 2, as appropriate.

PUBLIC COPY
This document cannot be used to support any marketing authorization application and any extensions or variations thereof.

ZX008 (Fenfluramine Hydrochloride)
ZX008-1601 Clinical Study PA 4.0 (Japan) 25 July 2022

Table 1. Schedule of Assessments: Part 1

| Study Assessments – PART 1 | Baseline Period ^a | | | Titration + Maintenance Period | | | | | | | | EOS/ ET ^b | Post- Dosing ^l | Cardiac Follow- up ^c |
|--|------------------------------|--------------|-------------------------|--------------------------------|-----------------|----------------|--------------------|----------------|--------------|----------------|---------------|-------------------------|------------------------------|---------------------------------------|
| | Screening | 2 (Phone) | Random- ization 3 | Titration Period | | | Maintenance Period | | | | | | | |

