2.2.2 SECONDARY OBJECTIVES

The secondary objectives of Part 2 are:

- To assess the effect of ZX008 relative to the baseline on the following effectiveness measures:
 - The change in the frequency of seizures that result in drops
 - The change in the frequency of all countable motor seizures (GTC, TS, CS, AS, TA, FS, MS with a drop)
 - The change in the frequency of all countable seizures
 - The proportion of subjects who have a worsening or no change (i.e. $\leq 0\%$ reduction), $>0\%$, $\geq 25\%$, $\geq 50\%$, $\geq 75\%$, 100% reduction, and “near seizure freedom (ie, 0 or 1 seizures) in frequency of all countable seizures that result in drops, countable motor seizures that do not result in drops, all countable motor seizures, all countable seizures, and all countable seizures that do not result in drops
 - Number of seizure-free days, defined as 1) days with no countable seizures and 2) days with no seizures that result in drops
 - Longest interval between seizures that result in drops

ZX008 (Fenfluramine Hydrochloride)
ZX008-1601 Clinical Study PA 4.0 (Japan) 25 July 2022

- To evaluate the effect of ZX008 on the following endpoints:
 - Clinical Global Impression – Improvement rating, as assessed by the principal investigator
 - Clinical Global Impression – Improvement rating, as assessed by the parent/caregiver

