After 12 months in Part 2, seizure diaries are not required. Rather, based on discussions with the parent/caregiver, clinical evaluation, and review of any documentation provided by the caregivers, investigators will assess the percent improvement in seizure burden on a 5-point scale: <25%, ≥25%, ≥50%, ≥75%, 100% [ie, seizure-free] improvement.

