3. The investigator prepares a case history and rationale for continuation to be submitted to the IDSMC for review, including consideration of effects on seizures and comorbidities.
4. The cardiac reviewers (from the central reader, and potentially ICAB) prepare an evaluation of the cardiopulmonary risks and proposed monitoring plan if applicable, for submission to the IDSMC.
5. IDMSC will review the submissions from the Investigator and cardiac central reader and unblind the subject treatment if warranted.
6. IDSMC makes a determination of appropriate path, including the possible outcomes:
 - a. Discontinue study medication
 - b. Increase frequency of ECHO and ECG monitoring
 - c. Add additional ECG and/or ECHO measures to be monitored
 - d. Reduce the dose of study medication

Level 3:

1. The investigator will evaluate efficacy to date based on study diaries and consult with the parent/guardian, and determine whether the achieved benefit justifies the consideration of continuing study treatment by the IDSMC. MINIMAL efficacy criteria for IDSMC consideration:
 - a. Seizures must be more than 75% improved (number of motor seizures per 28 days) on treatment over baseline, and improvement must be consistent.
 - b. The number, type, duration, and distribution of seizures at baseline should be of a severity, which justifies the risks of cardiopulmonary complications, considering the subject's age and overall health.
 - c. Subject has had reasonable trials (dose and duration) of other available anticonvulsants (eg, valproic acid, clobazam, topiramate), alone or in

ZX008 (Fenfluramine Hydrochloride)
ZX008-1601 Clinical Study PA 4.0 (Japan) 25 July 2022

combination, and not maintained the level of seizure control achieved with study medication.

2. If the investigator feels consideration of continued treatment is warranted considering benefit and potential risks, and the parent/guardian feels strongly that the child be maintained on the study medication when understanding the risks, the parent/guardian must sign a new consent, which describes the additional risks and the child should provide assent if possible.
 - a. If both of these conditions are not met, the subject is discontinued from treatment.
3. The investigator prepares a case history and rationale for continuation to be submitted to the IDSMC for review, which includes effects of study medication on seizures and comorbidities related to LGS.

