10.2.4.2 Effectiveness Analyses

Effectiveness will be assessed by the change from baseline (prior to randomization into Part 1) in DSF. The DSF per 28 days will be calculated as the number of seizures recorded divided by the number of days in the period and multiplied by 28. The change in DSF during the OLE Treatment Period will be calculated as the difference between DSF during the OLE and the baseline DSF measured prior to randomization in Part 1. The percent change in DSF is the change in DSF between OLE and Baseline / DSF during Baseline x 100. Both the mean and median percent change in DSF will be presented and the statistical significance of the percent change will be assessed using a Wilcoxon signed-rank test. Other secondary assessments will be compared to baseline from prior to Part 1, or by visit throughout Part 1 and Part 2, as appropriate.

For subjects continuing in Part 2 past Visit 22, effectiveness will be assessed by investigator rating of overall change in seizure frequency (<25%, ≥25%, ≥50%, or ≥75%, 100% (seizure-free) improvement compared to last visit).

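### After Month 12 of Part 2 the only required seizure-frequency measure is an improvement rating against the last visit with no worsening class, so change from the pre-randomization baseline cannot be recovered

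*Protocol*

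**What the plan says.** The Part 2 secondary objectives in Section 2.2.2 are "To assess the effect of ZX008 relative to the baseline on the following effectiveness measures". They include proportions of subjects by percent reduction, with one class for worsening or no change (a reduction of 0% or less).

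For diary data, the reference is the baseline before randomization into Part 1 (Section 10.2.4.2). The synopsis limits that comparison in time: "The change in DSF during the first 12 months of" the Part 2 treatment period. Section 7.1.1 then states: "After 12 months in Part 2, seizure diaries are not required".

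From that point the seizure measure is an investigator rating. It is described in three places:

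- Section 7.1.1: "investigators will assess the percent improvement in seizure burden on a 5-point scale: <25%, ≥25%, ≥50%, ≥75%, 100% [ie, seizure-free] improvement". No reference point is given.
- Table 2, note r: the same scale, again with no reference point.
- Section 10.2.4.2: "investigator rating of overall change in seizure frequency (<25%, ≥25%, ≥50%, or ≥75%, 100% (seizure-free) improvement compared to last visit". This is the only place that names an anchor.

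Section 8.9.1 has the investigator evaluate efficacy from study diaries when an echocardiogram finding reaches Level 2 or Level 3. For Level 3 it adds: "Seizures must be more than 75% improved (number of motor seizures per 28 days) on treatment over baseline".

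**The concern.** The post-Month-12 scale keeps the 25, 50, 75 and 100% cut-points of the Section 2.2.2 proportions. However, the analysis section changes the reference from baseline to the last visit, and the class for worsening or no change is dropped. A table of these ratings would look like responder proportions against baseline without being so.

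A subject whose benefit is maintained shows no further improvement since the last visit and so falls in the lowest class. That class also takes in any degree of deterioration. With no required diary behind it, the rating is all the seizure-frequency information the plan guarantees. Annual extensions rest partly on a review of effectiveness, and the echocardiogram review refers to diaries and to improvement over baseline, so the reference point matters beyond the table.

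**Working it through.** The plan states no figure to reproduce here. The check puts assumed seizure courses through the stated classes.

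**Inputs.** Classes and anchor come from Section 10.2.4.2, and the baseline reference from Section 2.2.2. The baseline of 80 drop seizures per 28 days and the courses below are illustrations, not figures from the protocol.

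**Formulas.** Improvement versus last visit = 1 − current/previous. Improvement versus baseline = 1 − current/80. The class is the highest threshold met.

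| Course | Versus last visit | Class | Versus baseline | Class |
|---|---|---|---|---|
| Stable: 20, 20, 20 | 1 − 20/20 = 0% each time | <25% | 1 − 20/80 = 75% | ≥75% |
| Full relapse: 20, 80, 80 | 1 − 80/20 = −300%, then 0% | <25%, <25% | 1 − 80/80 = 0% | <25% |
| Relapse, part regained: 20, 80, 40, 40 | −300%, 50%, 0% | <25%, ≥50%, <25% | 0%, 50%, 50% | <25%, ≥50%, ≥50% |
| Slow gain: 64, 51.2, 40.96, 32.8 | about 20% each time | <25% throughout | 36.0%, 48.8%, 59.0% | ≥25%, ≥25%, ≥50% |
| Seizure-free: 0, 0, 0 | 0/0, undefined | 100% label can still be chosen | 100% | 100% |

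The first two rows leave identical records under the last-visit rule, although one subject has kept a 75% reduction and the other has lost it all. In the third row the best rating falls at the visit where the subject is only partly recovering.

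**Can the ratings be chained back?** A rating of <25% says only that current/previous is above 0.75. After k such ratings, the ratio to the Month 12 frequency is above 0.75^k, with no upper limit:

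- k = 1: above 0.75
- k = 4: above 0.75^4 = 0.316
- k = 12: above 0.75^12 = 0.032

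Twelve is the number of in-clinic ratings for a subject who changes to six-monthly visits after Month 24: Months 15, 18, 21 and 24 (4), then Months 30 to 72 every 6 months (8). The interval behind the last visit therefore changes from 3 to 6 months. Section 6.2.5 also places phone visits between the later clinic visits without a seizure rating, so which visit is meant is not fixed.

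**Extent.** 72 − 12 = 60 months of possible Part 2 treatment have no required diary.

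**The case against.** The strongest reply is that effectiveness after Month 12 does not rest on this rating alone. CGI-I by investigator and by caregiver continues at the in-clinic visits and at end of study (Table 2, Sections 6.2.5 and 6.2.6). It is anchored to the Baseline Period, has three worsening grades (Section 7.1.2), and is a named Part 2 secondary endpoint. Seizure exacerbation is also recorded as an adverse event (Section 8.1.1), and clinically significant worsening is a discontinuation criterion (Section 4.5). All of this stands. It limits the loss to seizure frequency, but a global impression or an adverse event report cannot supply the percent-reduction classes of Section 2.2.2.

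A second reply is that the anchor is unsettled. Two of the three descriptions name none, so sites may be rating against baseline, and the CRF is not shown. That is fair: the result in the table holds under the Section 10.2.4.2 wording. The silence elsewhere is a defect too, because ratings made against different references cannot be pooled.

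A third reply concerns overlap. Each threshold contains those above it, but a 5-point scale implies one choice, naturally the highest threshold met. This is a matter of wording only.

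Three stronger readings are tempting, and the documents do not support them:

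- **Maintained responders are counted as failures.** The protocol defines neither failure nor responder on this scale, and a subject who stays seizure-free can still be rated 100%.
- **The extension years cannot show maintenance or loss of effect at all.** CGI-I can show either, in global terms.
- **Echocardiogram review after Month 12 has no seizure input.** Diaries are not required, but they are not forbidden. The investigator may use caregiver discussion and any documentation caregivers provide (Section 7.1.1), and the Amendment 4.0 rationale expects caregivers to go on reporting seizure data. Efficacy to date also includes the earlier diaries.

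**Conclusion.** The point holds in this form. Section 10.2.4.2 ties the only required post-Month-12 seizure-frequency measure to the last visit, against a baseline-relative objective, while Section 7.1.1 and Table 2 note r leave the anchor open. Under the stated rule, stable responders who are not seizure-free cannot be told apart from subjects who have relapsed. Worsening cannot be told from no change, and seizure-frequency change from the pre-randomization baseline cannot be reconstructed.

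The conclusion rests on the Section 10.2.4.2 wording being what is applied and analysed. The seizure counts used to show it are assumed, but the identity of the two records does not depend on them.

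The consequence is limited. It touches a secondary objective of an open-label extension whose primary objective is safety. In this version that extension's schedule (Table 2) covers Cohort B, planned at 30 to 50 randomized subjects. The Part 1 primary analysis is unaffected. The change should be made, but nothing confirmatory depends on it.

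**What to change.** 1. In Section 10.2.4.2, Section 7.1.1, Table 2 note r and the CRF, state that the rating is relative to the pre-randomization baseline, as for the diary endpoint and CGI-I.
2. Use mutually exclusive classes: worse than baseline; no change; >0 to <25%; 25 to <50%; 50 to <75%; 75 to <100%; 100%. The first two together give the worsening-or-no-change class of Section 2.2.2.
3. Establish which anchor was used for ratings already collected, and report those made against the last visit, or against an unknown reference, separately from those made against baseline.
4. As a separate matter, reconcile Section 8.9.1, which relies on study diaries and improvement over baseline, with the end of required diaries at Month 12. No clinical rule is proposed here.

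The cost of items 1 to 3 is wording in three places, one CRF item for future visits, a query to sites about past ratings and a split table. No visit, assessment or subject is added.

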10.2.5 ANALYSES PROVIDED TO AN INDEPENDENT DATA AND SAFETY MONITORING COMMITTEE

A safety oversight monitoring plan will be in place with an IDSMC evaluating data from the subjects. Details will be provided in the IDSMC charter. The IDSMC's primary responsibility is to ensure that study subjects are not exposed to unanticipated harm that could have been prevented by timely review and intervention. The IDSMC is established to review safety data at predefined time points, and to recommend to the sponsor whether to continue, modify, or terminate the study as necessary. The IDSMC is composed of expert permanent members who cover relevant specialties. The IDSMC members may request assistance from a number of additional and ad hoc members if needed.

11. ETHICAL & REGULATORY CONSIDERATIONS

11.1 ETHICAL CONSIDERATIONS

The procedures set out in this study protocol are designed to ensure that the sponsor and the investigator abide by the principles of the current ICH GCP guideline on the conduct, evaluation and documentation of this study, as described in ICH Topic E6 Guideline. ICH GCP is an international ethical and scientific quality standard for designing, conducting, recording, and reporting studies that involve the participation of human subjects. Compliance with this standard provides public assurance that the rights, safety, and well-being of study subjects are

ZX008 (Fenfluramine Hydrochloride)
ZX008-1601 Clinical Study PA 4.0 (Japan) 25 July 2022

protected and consistent with the principles of the Declaration of Helsinki, and that the clinical study data are credible.

The study will also be carried out according to all applicable international and national regulatory requirements.

The sponsor and the investigator must inform each other (eg, during a study initiation visit, via e-mail, etc) that all ethical and legal requirements have been met before the first subject is enrolled into the study.

11.2 INFORMED CONSENT

The investigator is responsible for obtaining a subject's written informed consent to participate in the study.

A Subject Information Sheet and a master ICF will be prepared by the sponsor according to the provisions of ICH GCP and local legal requirements.

All subjects will be informed that the study will be registered in the public database at ClinicalTrials.gov in accordance with the FDA Amendments Act of 2007 (Section 12.3).

Before undergoing screening procedures for possible enrollment into the study, subjects must be informed, in an understandable form, about the nature, scope, and possible consequences of the study. This information must be given orally to subjects by a physician or medically qualified person (according to applicable regulatory requirements) who is well informed about the nature, scope, and possible consequences of the study. Written information about the study will also be provided in a Subject Information Sheet. The date on which this oral and written information on the study was provided to the subject, and by whom it was provided, must be documented in the ICF.

As specified in ICH GCP Section 4.8 and the US 21CFR Section 50.25, the informed consent discussion must emphasize that participation in the study is voluntary and that subjects have the right to withdraw their consent at any time without giving a reason and without any disadvantage for their subsequent care.

Subjects must be given ample time and opportunity to inquire about details of the study and to consider their participation in the study. If, after reading the Subject Information Sheet and the ICF, consent is given to participate in the study, then the ICF must be signed and personally dated by the subject and the person conducting the informed consent discussion (and an impartial witness, if required). The subject will be provided with a copy of the signed ICF.

Verification of the signed ICF will be recorded in the subject's eCRF. The original signed ICF will be filed with the subject's records and/or in the Investigator Study File.

The Subject Information Sheet and ICF have to be approved by the IEC/IRB before they can be used in the study.

The Subject Information Sheet and ICF must be revised whenever important new information becomes available that may be relevant to the subject's consent. Any revision of these documents must be approved by the IEC/IRB before they can be used in the study. Subjects must be informed in a timely manner if new information becomes available that may be relevant to their willingness to continue participation in the study. The communication of this

ZX008 (Fenfluramine Hydrochloride)
ZX008-1601 Clinical Study PA 4.0 (Japan) 25 July 2022

information should be documented by having all parties concerned sign and personally date the revised ICF.

Subject or Subject's Legally Acceptable Representative Unable to Read

If a subject is unable to read, or if a legally acceptable representative is unable to read, an impartial witness should be present during the entire informed consent discussion. After the ICF and any other written information provided to the subject, parent or guardian has been read and explained to the subject or the subject's legally acceptable representative, and after the subject or the subject's legally acceptable representative has orally consented to the subject's participation in the study and, if capable of doing so, has signed and personally dated the ICF, the witness should also sign and personally date the ICF. By signing the ICF, the witness attests that the information in the ICF and any other written information was accurately explained to, and apparently understood by, the subject or the subject's legally acceptable representative, and that informed consent was freely given by the subject or the subject's legally acceptable representative.

Assent for Subjects Under the Age of Consent (Pediatric Subjects)

All subjects are under the age of consent (ie, pediatric subjects under 18 years of age); the written informed consent of a legally acceptable representative is required. Pediatric subjects who can understand the nature, scope, and possible consequences of the study must also give their assent, orally and/or in writing via the assent document, as appropriate. After the ICF and any other written information to be provided to subjects has been read and explained to the subject and the subject's legally acceptable representative, and after the subject and the legally acceptable representative have orally consented to the subject's participation in the study and, if capable of doing so, the subject has signed and personally dated the assent document, the legally acceptable representative should sign and personally date the ICF. By signing the ICF, the legally acceptable representative attests that the information in the ICF and any other written information was accurately explained to, and apparently understood by, the subject, and that assent was freely given by the subject.

11.3 REGULATORY CONSIDERATIONS AND INDEPENDENT ETHICS COMMITTEE/INSTITUTIONAL REVIEW BOARD

The sponsor (or delegate) will submit the appropriate documents to all applicable competent regulatory authorities and IEC/IRBs, and will await all relevant approval before enrolling any subjects into the study. Written approval should mention the study protocol by study title, study number, and version date.

This study will be conducted under Investigational New Drug (IND) Application and documented in accordance with the applicable regulatory guidelines and requirements.

The sponsor (delegate) will ensure that the investigators conduct the study as stipulated in this study protocol and in accordance with all applicable regulatory requirements. The sponsor (delegate) is obliged to obtain evidence of the investigator's qualification to perform the clinical study. Therefore, the investigator has to provide a signed and dated copy of his or her professional curriculum vitae (prepared no more than 2 years beforehand and preferably written in English) before the start of the study, including information on his or her experience in conducting

ZX008 (Fenfluramine Hydrochloride)
ZX008-1601 Clinical Study PA 4.0 (Japan) 25 July 2022

clinical studies according to ICH GCP and other applicable regulatory requirements.

Written notification of the identity and occupation of the members of the IEC/IRB is also required by the sponsor (delegate). Should the IEC/IRB be unwilling to provide this information, a letter stating that the committee was constituted in accordance with applicable regulatory requirements should be provided.

